US IMAGING						
US-score PsA-SIR		X		X	X	X
CR IMAGING						
X ray (hands-feet)		X			X	X
ADVERSE EVENTS			X	X	X	X

STATISTICAL ANALYSIS PLAN

VARIABLES: OUTCOME MEASURES

PRIMARY:

- MDA at 6 months

SECONDARY

- MDA at 12 months, sustained MDA at 6 AND 12 months
- DAPSA <3.3 at 6 months, 12 months, 6 AND 12 months
- Δ mSvH 0-12 and 0-24 months
- Δ HAQ 0-12 and 0-24 months
- Δ PSAID 0-12 and 0-24 months
- US-score PsA-SIR damage subscore at 0-6-12 months

US PREDICTORS

- US-score PsA-SIR
- US-score PsA-SIR inflammation subscore
- US-score PsA-SIR damage subscore

CLINICAL PREDICTORS

Based on the relevant literature clinical variables to be considered in the model include:

- Demographic and environmental factors:
 - Age
 - Gender
 - Smoking
 - BMI
- Clinical factors:
 - subset of PsA
 - time from symptoms onset to diagnosis
 - disease duration
 - disease activity (DAPSA and BASDAI)
 - HAQ score
 - tender joints / pain
 - comorbidities (FM, MetS)
- Serological factors:
 - Acute phase reactants
- Therapy factors:
 - Treatment (NSAIDs, steroids, DMARDs)

DESCRIPTIVE ANALYSES

Descriptive data will be provided for all outcomes according to data type; number of patients (N), mean, standard deviation (for interval data), median 25% and 75% quartiles (for ordinal data). Frequency (absolute and relative) distributions will be provided for categorical data. Two-sided p-values will be presented throughout.

PRIMARY ENDPOINT ANALYSIS

Prediction of 6 months MDA will use multivariate adjusted logistic models. A baseline model will include all the clinical variables. US predictors will be added as covariates to the clinical variables, assuming an additive model. The derived β coefficients were used to calculate prognostic indices, thereby creating weighted prediction models.

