The simulations were carried out using the procedure `rocsz` Stata (by M. Pepe)³⁰, which allows to determine the power to detect an improvement in the ROC curve. The procedure requires the specification of the percentage of false positive and true positive both for the null hypothesis is for the alternative hypothesis and the percentage of positive / diseased.

Using the command `rocsz 0.7 0.2, na (150) ndb (100) tnull (0.7) fnull (0.4)` of Stata, 250 patients are sufficient to evaluate the performance of a model (and its ROC curve) with 90% power and 5% alpha. Specifically, we have assumed a 70% and a 20% of subjects true positives and false positives, respectively, according to the alternative hypothesis, a 70% and a 40% of subjects true positives and false positives, respectively, according to the null hypothesis, and a percentage of diseased of 60% (150 of 250 subjects).

Under the assumption of maximum attrition of 20%, the sample size will be increased to 300 patients. The same sample size is sufficient to precisely estimate a logistic model of achievement of a MDA (probability of 0.4 at 6 months) with 10 predictors (rule of thumbs).⁽³¹⁾

Based on the pre-study activities, 35-40 centres will be involved, 15 tertiary and 20-25 secondary rheumatology centres. Assuming 4 eligible patients/months for tertiary and 1/month in secondary centres, a 40% of enrolment rate, about 30 patients/months are expected.

ETHICS

This study will be conducted in accordance with all applicable laws and regulations including, but not limited to, the International Conference on Harmonisation (ICH) Guideline for Good Clinical Practice (GCP), EU guidelines and the ethical principles that have their origins in the Declaration of Helsinki. The institutional review board (IRB)/independent ethics committee (IEC) must review and approve the protocol and informed consent form before any subjects are enrolled. Before any protocol-required procedures are performed, the subject must sign and date the IRB/IEC-approved informed consent form.

Clinical data (including AEs and concomitant medications) will be entered into a validated data capture system provided by the Italian Society for Rheumatology. The data system will include password protection and internal quality checks, such as automatic range checks, to identify data that appear inconsistent, incomplete, or inaccurate.

PUBLICATION RULES

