The study protocol will be submitted for publication and all the results of all the analyses stored at the <https://osf.io/f8mrg>.

Following completion of the study, the full results of this research will be published in a peer reviewed scientific journal. An Open Access publication policy will be applied.

As this is a multi-centre study, the results from individual centres must not be published prior to the publication of the entire study results and without prior agreement of the Steering Committee. For avoidance of doubt the first publication must be the responsibility of the Chief Investigators. A main authorship will be offered to all Local investigators who achieve the minimum target of 20 patients with complete clinical and ultrasound data at baseline and >80% of complete data at 6 months. All the other Investigators not reaching these criteria will be included in the collaborator's list or in the acknowledgements according to the table below.

Number of patients	Sonographer	Clinician
20	Author	Author
10-19	Author	Collaborator
5-9	Collaborator	Acknowledgment
<5	Acknowledgment	

All the investigators will be able to apply to investigator-initiated-studies using the entire data-set, being able to define the authorship according to International Committee of Medical Journal Editors Recommendations.⁽³²⁾

-
- ¹ Moll JM, Wright V. Psoriatic arthritis. *Semin Arthritis Rheum*. 1973;3(1):55–78
- ² Coates LC, Helliwell PS. Validation of minimal disease activity criteria for psoriatic arthritis using interventional trial data. *Arthritis Care Res*. 2010 Jul 1;62(7):965–9
- ³ Gossec L, Smolen JS, Ramiro S, Wit M de, Cutolo M, Dougados M, et al. European League Against Rheumatism (EULAR) recommendations for the management of psoriatic arthritis with pharmacological therapies: 2015 update. *Ann Rheum Dis*. 2015 Dec 7;annrheumdis – 2015–208337
- ⁴ Sokoll KB, Helliwell PS. Comparison of disability and quality of life in rheumatoid and psoriatic arthritis. *J Rheumatol*. 2001 Aug;28(8):1842–6
- ⁵ Eder L, Thavaneswaran A, Chandran V, Cook RJ, Gladman DD. Obesity is associated with a lower probability of achieving sustained minimal disease activity state among patients with psoriatic arthritis. *Ann Rheum Dis*. 2015 May;74(5):813–7

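### Enrolling 300 protects 250 evaluable patients only up to 16.7% loss; at the stated 20% maximum it leaves 240

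*Combined protocol and SAP*

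**What the plan says.** The Sample Size section states that "250 patients are sufficient to evaluate the performance of a model (and its ROC curve) with 90% power and 5% alpha". The underlying Stata command is given as "rocsz 0.7 0.2, na (150) ndb (100) tnull (0.7) fnull (0.4"), and the text describes its group sizes as "a percentage of diseased of 60% (150 of 250 subjects"). Here 'diseased' means not responding to therapy.

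The allowance for loss follows in one sentence: "Under the assumption of maximum attrition of 20%, the sample size will be increased to 300 patients". No formula is given, and no visit is named at which the 20% applies.

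The primary outcome is listed as "MDA at 6 months", and under Primary Endpoint Analysis the plan says "Prediction of 6 months MDA will use multivariate adjusted logistic models". Follow-up runs to 24 months. I found no rule for replacing patients, no method for a missing 6-month MDA, and no statement that fewer than 250 evaluable patients would be enough.

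**The concern.** The only purpose of raising 250 to 300 is to have 250 left after the planned loss. Adding 20% of the evaluable number does not achieve this, because the loss is taken from the larger, enrolled number. At the plan's own maximum, both the total of 250 and the 150/100 split entered in the command are missed. The power quoted then belongs to a larger data set than the one 300 enrolled patients are certain to provide.

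A reader who takes the section at face value will believe that the power statement survives a 20% loss. It is secured only up to a lower loss, which the plan does not state.

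**Working it through.** **Inputs, all from the Sample Size section:** 250 evaluable (150 not responding, 100 responding); maximum attrition d = 0.20; 300 enrolled; true-positive rate 0.7 under both hypotheses; false-positive rate 0.4 under the null and 0.2 under the alternative; alpha 5%. Sidedness is not stated there. Descriptive Analyses says "Two-sided p-values will be presented throughout", so two-sided is used first.

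**Step 1: reproduce the plan's figure.** 250 × (1 + 0.20) = 300. This matches exactly.

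**Step 2: the number that keeps 250 after a 20% loss.** 250 / (1 − 0.20) = 312.5, so 313. The plan is 13 short.

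**Step 3: what 300 delivers.**
- At 20% loss: 300 × 0.80 = 240, which is 10 below 250 (10/250 = 4%).
- Split at 60/40: 240 × 0.6 = 144 and 240 × 0.4 = 96.
- Break-even: 1 − 250/300 = 16.7%.
- Either side of it: 15% loss leaves 255; 18% leaves 246.

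**Step 4: what the 10 patients cost in power.** The plan's command was not run. As a stand-in, take the false-positive rate f at a true-positive rate of t = 0.7, assuming a binormal ROC curve with slope parameter 1:

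SE(f)² = f(1 − f)/n₀ + r² · t(1 − t)/n₁, with r = φ(Φ⁻¹(f)) / φ(Φ⁻¹(t))

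Here n₁ is the number not responding and n₀ the number responding. r is 0.805 at f = 0.2 and 1.111 at f = 0.4.

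| | 150/100 | 144/96 |
|---|---|---|
| SE under the alternative, SE₁ | 0.0501 | 0.0511 |
| SE under the null, SE₀ | 0.0643 | 0.0656 |

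Four versions of the power at two-sided 5%:

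| Version | Formula | 150/100 | 144/96 | Loss (points) |
|---|---|---|---|---|
| Alternative SE | Φ(0.2/SE₁ − 1.96) | 97.9% | 97.5% | 0.4 |
| Null SE for the cut-off, alternative SE for power | Φ((0.2 − 1.96·SE₀)/SE₁) | 93.0% | 91.9% | 1.1 |
| Null SE throughout | Φ(0.2/SE₀ − 1.96) | 87.6% | 86.2% | 1.3 |
| Logit scale | Φ(0.981/(SE₁/0.16) − 1.96) | 88.0% | 86.7% | 1.3 |

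In the last row, 0.981 = logit(0.4) − logit(0.2) and 0.16 = 0.2 × 0.8. Two versions stay above 90% at both sizes and two are below 90% at both. None crosses 90% because of the 10 patients.

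**The case against.** Nobody disputes the arithmetic. The case on the other side concerns whether it matters.

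- **Timing.** The 20% is called a maximum and no visit is named. If it covers all 24 months, loss by 6 months may well be under 16.7%, and then at least 250 remain. This stands, and the conclusion is conditional on it. It also shows why the visit should be stated.
- **'Sufficient' is not 'minimum'.** The plan does not say that 240 would be too few, and round inputs of 150 and 100 do not suggest a search for the smallest adequate number. This stands: a shortfall against 250 is not proof that 90% is missed.
- **Method matters more than the 10 patients.** At 150/100 the four approximations run from 87.6% to 97.9%, about 10 points, against a loss of at most 1.3. At one-sided 5%, all four stay above 90% with 144/96 (98.8%, 96.4%, 92.0% and 92.3%). This stands too.
- **A larger fall can be produced by simulation.** One logit-scale, two-sided simulation gave 89.9% at 150/100 and 86.0% at 144/96. Another gave 93.0% at 150/100, 91.4% at 148/98 and 92.7% at 144/96. Because the second series does not move in one direction, differences of this size may come from the discreteness of the empirical quantiles. They should not be used to enlarge the point.

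None of this makes 300 the right answer to a 20% loss from enrolment.

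**Conclusion.** The concern holds and is minor. As written, the section presents 300 as the allowance for up to 20% attrition, but 300 keeps the 250 patients behind the power statement only up to 16.7%. If the full 20% is lost by 6 months, 240 remain: 10 evaluable patients short, equivalent to 13 at enrolment.

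The 144/96 split assumes that loss is unrelated to MDA status. The power cost of 0.4 to 1.3 points assumes a binormal curve and a two-sided test, and only approximates the plan's command. Whether the command itself gives less than 90% at 240 is neither shown nor excluded.

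**What to change.** Keep 300 and replace the attrition sentence with wording such as:

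> 300 patients will be enrolled. This gives 250 evaluable at 6 months if attrition by then is at most 16.7%, and 240 (about 144 not in MDA and 96 in MDA, if loss is unrelated to MDA status) if it is 20%.

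Then:

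1. State the visit to which the 20% refers.
2. Rerun the plan's command with 144 and 96, and quote that power beside the figure for 150 and 100. State whether alpha is one- or two-sided.

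The cost is two or three sentences and one rerun, with no extra patients. If the sponsor would rather secure 250 at a 20% loss, the enrolment figure is 313.
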